3.3.6. Imputation of Alphanumeric Data

Should there be instances where laboratory data are recorded as for example, “<0.1” or “>10”, the data will be imputed for the purpose of quantitative summaries. The data will appear in data listings unchanged.

For incorporation in quantitative summaries, the following imputation rules will be employed:

The limit of quantitation will be increased by one level of precision in the direction of the symbol that precedes the value. For example, “< 0.1” will be imputed to “0.09”, while “>0.1” will be imputed to “0.11”, and “>10” will be imputed to “10.1”. Value reported as “≤” or “≥” will be imputed similarly. For example, “≤ 0.1” will be imputed to “0.09”.

3.3.7. Presentations by Time Point

Nominal Time Points as obtained from the CRF or laboratory will be utilized for summary displays. If assessments are collected multiple times within a given nominal time point, the result closest to the scheduled time will be used for summary presentations. If two measurements have the same distance to the expected time, the earlier value will be used. If a scheduled assessment and an Unscheduled or Early Termination assessment are collected on the same day, the scheduled assessment will be used for summary presentations, unless

otherwise indicated by the sponsor. Unscheduled and Early Termination assessments will be windowed to a study visit using the analysis window described below in case the scheduled visit was not performed. All assessments will be presented in the listings.

Visit	Target Day	Window Days
3: Week 2	15	9 - 22
4: Week 4	29	23 - 36
5: Week 6	43	37 - 50
6: Follow-Up	57	51 - 64

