8. STUDY EVALUATIONS

8.1. Study Procedures

8.1.1. Overview

The [Time and Events Schedule](#) that follows the Synopsis summarizes the frequency and timing of efficacy, PK, PD, and safety measurements applicable to this study.

With the exception of fasting safety laboratory and pre-dose PK blood draws, all visit-specific efficacy assessments during any study visit should be conducted first, before other scheduled tests, procedures, or medical consultations planned for the patients at any specific visit.

A serum pregnancy test is required at Screening, Baseline, and the post-study follow-up visit for all women of childbearing potential. Additional urine pregnancy tests may be performed, as determined necessary by the investigator or required by local regulation, to establish the absence of pregnancy throughout the study.

During the study, including the end-of-study visit, the total blood volume to be collected from each patient will be 136.5 mL (Table 2).

These estimates are for required blood samples and do not include additional blood samples that may be collected at the investigator's discretion for drug level monitoring or other clinical laboratory tests deemed necessary for appropriate patient care in case of occurrence of adverse events.

Table 2: Estimated Blood Volume Drawn

Type of Sample	Volume per Sample (mL)	No. of Samples per Patient	Total Volume of Blood (mL) ^a
Safety			
Hematology	3.5	4	14
Chemistry	5.0	4	20
TSH and Serology ^b	8.5	1	8.5
PK	6	9	54
PD	15	2	30
Pharmacogenomic	10	1	10
Total blood volume drawn			136.5

^a Calculated as number of samples multiplied by amount of blood per sample.

^b Includes HBsAg, anti-HCV, and anti-HIV.

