9. PATIENT COMPLETION/WITHDRAWAL

9.1. Completion

A patient will be considered to have completed the study if he or she has completed assessments at Week 6 of the double-blind treatment phase. Patients who prematurely discontinue study treatment for any reason before completion of the double-blind treatment phase will not be considered to have completed the study. The investigational drug will not be available after the completion of the study.

9.2. Withdrawal from the Study and Replacement.

The patients have the right to withdraw from the study at any time for any reason, without the need to justify.

A patient will be withdrawn from the study for any of the following reasons:

- Patient withdraws consent.
- Lost to follow-up.
- Termination of the study.
- The investigator believes that for safety reasons (e.g., adverse event) it is in the best interest of the patient to stop treatment.
- The patient becomes pregnant.
- Failure to use an acceptable method of birth control.
- Significant deviation from the protocol.
- Occurrence of a treatment-related serious adverse event.
- Concurrent illness and requirement of a prohibited medication.
- The patient meets one of the following .stopping criteria:
 - Patient with significant increase in ALT [i.e., > 5 upper limit of normal (ULN)].
 - Patient with abnormal laboratory results with simultaneous increases of total bilirubin (> 2 ULN), ALT (> 3 ULN) and alkaline phosphatases (< 1.5 ULN).
 - Patient with sustained mean QTcF (calculated using Fridericia's formula) value > 500 msec (confirmed by a second ECG under strict resting position and at minimum at ½ hour distant from the first measurement).
 - Patient with sustained increase of more than 60 msec in the mean QTcF compared to Baseline (confirmed by a second ECG under strict resting conditions).

If a patient discontinues treatment before the double-blind phase ends, attempts to obtain end-of-treatment and follow-up assessments must be made. In case a patient is lost to

follow-up, every possible effort must be made by the study site personnel to contact the patient and determine the reason for discontinuation/withdrawal. The measures taken to follow-up must be documented. When a patient withdraws before completing the study, the reason for withdrawal is to be documented in the eCRF and in the source document. Study drug assigned to the withdrawn patient may not be assigned to another patient. Patients who withdraw will not be replaced.

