5.4.2. Clinical Laboratory Assessments

Descriptive summaries of selected (quantitative) clinical laboratory results and change from baseline will be presented by treatment group and visit. Laboratory abnormalities will be determined using pre-defined normal ranges. The number and percentage of patients experiencing TE clinically significant (CS) laboratory abnormalities as reported by the central laboratory, and potentially clinically significant (PCS) abnormalities for select parameters per the table below will be summarized by treatment group. Additionally, shifts in Laboratory values with reference to the normal range from Study Baseline to Week 6 will be summarized by treatment group.

Listings will be provided for patients with any laboratory results outside the reference ranges, as well as for patients with any CS and PCS (select parameters) laboratory results.

Criteria for Potentially Clinically Significant Laboratory Tests

Laboratory Parameter	SI Units	Conversion Factor^a	Traditional Units	PCS Criteria^b Low Values	PCS Criteria^b High Values
Hematology					
Hemoglobin	F	g/L	0.1	g/dL	< 100
	Male				< 120
Hematocrit	F	ratio	100	%	≤ 32% and ≥3% decrease from baseline
	Male				≤ 37% and ≥3% decrease from baseline
White cell count		10 ⁹ /L	1	10 ³ /μL	≤ 2.5
Eosinophils absolute cell count		10 ⁹ /L	1	10 ³ /μL	—
Neutrophils absolute cell count		10 ⁹ /L	1	10 ³ /μL	≤ 1.50
					≥ 15
					≥ 1.50
					≥ 12.0

Lymphocyte absolute cell count	10 ⁹ /L	1	10 ³ /μL	≤ 0.8	≥ 4.0
Platelet count	10 ⁹ /L	1	10 ³ /μL	≤ 75	≥ 700
Chemistry					
Albumin	g/L	0.1	g/dL	< 28	—
Alkaline phosphatase	U/L	1	U/L	—	≥ 2 × UNL
ALT	U/L	1	U/L	—	≥ 3 × UNL
AST	U/L	1	U/L	—	≥ 3 × UNL
Blood urea nitrogen	mmol/L	2.8011	mg/dL	—	> 1.4 × UNL
Calcium	mmol/L	4.008	mg/dL	< 1.97	> 2.77
Cholesterol	mmol/L	38.6698	mg/dL	—	> 7.75
Creatinine	μmol/L	0.0113	mg/dL	—	> 1.4 × UNL
Glucose, fasting	mmol/L	18.015	mg/dL	< 3.0	> 7.6 × UNL
Potassium	mmol/L	1	mEq/L	< 3.3	> 5.5
Sodium	mmol/L	1	mEq/L	< 130	> 150
Total bilirubin	μmol/L	0.0585	mg/dL	—	> 1.5 × UNL
Urinalysis					
Protein	—	—	—	—	≥ 2 +
Glucose	—	—	—	—	≥ 1 +

^a Conversion factor is the multiplication factor to convert from SI units to traditional units.

^b Criteria refer to SI units.

LNL = lower normal limit of laboratory reference range; PCS = potentially clinically significant; SI = *Le Système International d'Unités* (International System of Units); UNL = upper normal limit of laboratory reference range.

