5.4.4. Other Safety Analyses

Descriptive summaries of vital signs data including body temperature, pulse, respiratory rate, and blood pressure (systolic and diastolic) and respective changes from Baseline, will be presented by time point and treatment group. The number and percentage of patients with PCS vital signs per the table below, as determined in the eCRF, occurring post-baseline will

also be summarized by time point and treatment group. All vital signs will be listed with clinically significant values flagged, as well as for patients with any PCS results.

CRITERIA FOR POTENTIALLY CLINICALLY SIGNIFICANT VITAL SIGNS

Parameter	Flag	Criteria
		Observed Value
Systolic blood pressure (mm Hg)	High	≥ 150
	Low	≤ 90
Diastolic blood pressure (mm Hg)	High	≥ 100
	Low	≤ 50
Pulse rate (bpm)	High	≥ 110
	Low	≤ 50
Temperature (°C)	High	≥ 38
	Low	< 35

Electrocardiogram (ECG) variables and their change from baseline will be summarized with descriptive statistics by time point and treatment group. ECG variables will include heart rate, PR interval, QRS interval, QT interval, and QTc interval corrected for heart rate using QTcF. QTcF values will also be tabulated for their absolute values and tabulated relative to baseline measurements in order to detect individual QTcF changes. Additionally, the number and percentage of patients with PCS values defined in the table below

Use header of the convention table for all relevant safety parameters.

Criteria for Potentially Clinically Significant ECG Parameters

Parameter	Flag	Criteria	
		Observed Value	Change from Baseline or Observed Value
Heart Rate (bpm)	High	> 110	
	Low	≤ 50	

QTcF ^a Interval (msec)	High Male	> 450	30-60, > 60, > 500
	High Female	> 470	
QRS Interval (msec)	High	> 120	
PR Interval (msec)	High	> 220	

^a QTc interval (Fridericia's) is derived as: $QTcF = QT \text{ Interval (msec)} / (RR \text{ (msec)/1000})^{1/3}$

For these summaries, worst-case assignments will be made to ensure patients with such values are not counted more than once. For example, a patient with QTcF interval > 500 msec will count once in the > 500 msec category and will not appear in the > 450 or > 480 msec categories. Similar conventions will be used for the 30 to 60 and > 60 msec categories. All ECG analyses will be based on the average of triplicate measurements.

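### SAP 3.3.7 drops abnormal extra readings from the by-time-point vital-sign counts and leaves unclear whether they count in the laboratory and QTcF abnormality tables

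*SAP*

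**What the plan says.** SAP 3.3.7 sets the default: "Nominal Time Points as obtained from the CRF or laboratory will be utilized for summary displays". Three selection rules follow.

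- With several results at one nominal time point, "the result closest to the scheduled time will be used for summary presentations". A tie goes to the earlier value.
- If a scheduled and an Unscheduled or Early Termination result fall on the same day, "the scheduled assessment will be used for summary presentations", unless the sponsor indicates otherwise.
- Unscheduled and Early Termination results are "windowed to a study visit using the analysis window described below in case the scheduled visit was not performed".

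The section adds that listings show everything. It makes no separate provision for safety data.

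The abnormality summaries are defined elsewhere:

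- **Laboratory (SAP 5.4.2).** Counts of patients with clinically significant (CS) abnormalities, and "potentially clinically significant (PCS) abnormalities for select parameters per the table below will be summarized by treatment group". No visit is attached.
- **Vital signs (SAP 5.4.4).** Counts of patients with post-Baseline PCS values will "also be summarized by time point and treatment group". The corresponding tables in SAP 9 (14.3.5.2.1 and 14.3.5.2.2) are titled as occurring post-Baseline, without mention of time point.
- **ECG (SAP 5.4.4).** Each patient is placed once, in the worst QTcF category. The eligible ECGs are not named.

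The protocol expects tests outside the schedule. Section 8.1.1 allows for "other clinical laboratory tests deemed necessary for appropriate patient care in case of occurrence of adverse events", section 8.1.3.2 for repeats of abnormal laboratory results, and section 9.2 for a confirmatory ECG.

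**The concern.** Extra tests are usually done because of a symptom or an earlier abnormal value, so they are more likely than routine tests to be abnormal. A rule that takes the value nearest the planned day, and sets extra results aside once the planned visit has happened, suits a table of means by visit. For a table meant to show how many patients ever crossed a safety threshold, it selects against the values of interest.

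The rates at stake are those promised in Protocol 10.8.3 and 10.8.4: percentages of patients beyond clinically important vital-sign limits and beyond QTc thresholds. Neither section restricts these to scheduled tests. Where the SAP is silent, two programmers could follow it faithfully and produce different counts. That choice should be settled before unblinding.

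**Working it through.** There is no planned figure to reproduce. The check applies the selection rule to the schedule and then to each table.

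**Inputs**

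- Post-dose schedule (SAP 1.2; Protocol Time and Events Schedule): chemistry at Visit 5/Early Withdrawal (Day 43) and Visit 6 (Day 57); ECG at Visit 4 (Day 29), Visit 5/Early Withdrawal and Visit 6; vital signs at Visits 3, 4, 5/Early Withdrawal and 6.
- Analysis windows (SAP 3.3.7): Visit 3, Days 9–22; Visit 4, Days 23–36; Visit 5, Days 37–50; Visit 6, Days 51–64.
- PCS limits: systolic pressure at or below 90 mm Hg (SAP 5.4.4); ALT at or above 3 times the upper normal limit (SAP 5.4.2).
- Planned size: 81 patients per dose (SAP 3.1).

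**1. Vital signs.** A patient attends Visit 3 on Day 15 with normal pressure. On Day 20 an extra reading is at or below 90 mm Hg. Day 20 lies in the Visit 3 window, but Visit 3 was performed, so the reading is not assigned to it. In a count made by time point, the patient has no PCS value at Visit 3.

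**2. Chemistry.** Days before the Week 6 window: 36 − 2 + 1 = 35 (Days 2–36). None holds a scheduled chemistry test.

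- Days 2–8 (7 days) fall in no window, so a result there can never be assigned to a visit.
- Days 9–36 (28 days) fall in the Visit 3 and Visit 4 windows. A result there is assigned only if that visit was missed, although neither visit includes chemistry.
- Check: 7 + 28 = 35.

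**3. Early termination.** Visit 3 takes place on Day 15. The patient stops on Day 20, and the early-withdrawal ALT exceeds the PCS limit. Day 20 points to Visit 3. Visit 3 was performed, without a laboratory test, so the rule assigns the ALT to no visit. The post-study visit comes about two weeks later (20 + 14 = Day 34). If ALT has fallen by then, that lower value is the only post-dose ALT in the by-visit table.

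**4. Effect by table**

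| Summary | Basis stated in the SAP | Extra result when the visit was performed |
|---|---|---|
| Laboratory, vital-sign and ECG values by visit | Visit or time point | Left out |
| PCS vital-sign counts | Time point in the text; post-Baseline in the table titles | Left out under the text; unclear from the titles |
| Laboratory CS/PCS counts | Treatment group | Not stated |
| QTcF categories | Worst category per patient | Not stated |
| Listings | All assessments | Included |

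**5. Size of one lost case.** 1/81 = 1.2%, against 0/81 = 0%. The one-sided 95% upper limit for 0/81 is 1 − 0.05^(1/81) = 0.036, or 3.6%. This illustrates a single case. The documents do not say how often extra tests will occur.

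**The case against.** The strongest reply is that 3.3.7 is headed as a rule for presentations by time point, so it need not reach patient-level counts. The table list in SAP 9 supports this: the descriptive laboratory, vital-sign and ECG tables are titled by time point, while the abnormality tables are not, and 14.3.5.4 on ECG abnormalities is titled as occurring post-Baseline. The worst-case wording for QTcF can also be read as covering any post-Baseline ECG.

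This stands in part. A reader might infer that an abnormal ALT or QTcF found at an extra test stays out of all the safety tables, or that the patient counts as normal. The documents do not support that: for these two counts the SAP is silent. Equally, silence is not inclusion. The worst-case sentence is there to prevent double counting across categories and does not say which ECGs are eligible.

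Four further points have force.

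- **Other routes.** Protocol 8.6 requires clinically relevant laboratory changes to be recorded as adverse events, which reach the tables in SAP 5.4.1. Out-of-range laboratory results and PCS results are listed. The signal is therefore not lost. But adverse event capture rests on investigator judgement, and listings give no rate by arm.
- **Confirmatory ECG.** One of the criteria in Protocol 9.2 is "Patient with sustained increase of more than 60 msec in the mean QTcF compared to Baseline", confirmed by a second ECG. The second ECG confirms a value already recorded. If the first was scheduled, 3.3.7 keeps it. This passage shows that extra ECGs will occur, not that a QTcF breach would be missed.
- **Early withdrawal.** A reader might infer that every chemistry or ECG result off the planned days is unscheduled. It is not: Visit 5 doubles as the Early Withdrawal visit, so planned tests can fall on other days. The difficulty with those results is the windowing rule in step 3.
- **Where the support lies.** Exclusion is clearest for vital signs, which are measured at every visit. The long schedule gaps concern chemistry and ECG, where the SAP is only unclear. The tables are descriptive, and the 3.6% upper limit for 0/81 already covers 1.2%.

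**Conclusion.** The point stands in two parts. First, as 5.4.4 is worded, abnormal extra readings are dropped from the PCS vital-sign counts when the scheduled visit took place; the text and the table titles do not agree on this. The same selection applies to the by-visit laboratory, ECG and vital-sign summaries, where it is acceptable for means but hides extremes. Second, the SAP does not settle whether extra results count in the laboratory CS/PCS counts and the QTcF categories.

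The consequence is possible understatement of threshold-based rates by arm. With 81 patients per dose, each omitted case is worth about 1.2 percentage points. The total effect cannot be estimated, because it depends on the number of extra tests and on how the programmer resolves the silence. The conclusion assumes that 3.3.7 is applied literally and that Early Termination results are windowed as it says. It does not affect the efficacy conclusions or any hypothesis test. It should be corrected before unblinding.

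**What to change.** - **SAP 3.3.7:** state that the selection rule applies only to by-visit descriptive statistics.
- **SAP 5.4.2 and 5.4.4:** state that CS and PCS counts and QTcF categories use the worst value per patient over all post-dose results, whether scheduled, unscheduled or early termination. Add a row for any time post-Baseline. Where PCS vital signs are also shown by time point, keep that as a secondary display so that text and table titles agree.
- **ECG:** the existing rule that analyses use the average of the triplicate needs no change.

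The cost is a few sentences and one extra row per table. No new data are needed, since all assessments are already to be listed. There is one small downside: patients tested more often have more chances to be flagged. Reporting the number of patients with any unscheduled test by arm lets the reader judge whether testing was balanced.

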3.3.8. Definitions and Terminology

Baseline Value

Baseline will be defined as the last valid evaluation done before the study drug administration on Day 1.

Day 1

Day 1 is the earliest day that study drug is first initiated.

Study Day

Study Day is defined relative to Baseline (Day 1). Thus, the study day of an event is calculated as:

For events occurring on or after Day 1, Study Day = event date – date of Day 1 + 1.

For events occurring prior to Day 1, Study Day = event date – dated of Day 1

Study Visit

Study Visit is the nominal visit as recorded on the CRF.

Last Dose of Study Drug

Last Dose of Study Drug is defined as the last date that the patient received study drug as determined by last date of dosing as recorded on the Study Drug Administration and Accountability CRF for Visit 5/Early Termination.

Days on Treatment

Days on treatment will be calculated as the number of days from the date of first dose to the date of last dose, inclusive.

Treatment Compliance

Treatment compliance during a specified period of time is defined as the total number of tablets taken by a patient during that time divided by the number of tablets prescribed during that time, multiplied by 100. The number of tablets prescribed during a specified period of time will be calculated as the number of days in that timeframe multiplied by the number of tablets prescribed per day.

Change from Baseline

Change from baseline for a given endpoint is defined as the Study Visit X value minus the Baseline Value.

MADRS Response

MADRS response is defined as a decrease from Baseline in MADRS total score of $\geq 50\%$.

Time to $\geq 50\%$ MADRS Improvement (Days)

Time to $\geq 50\%$ MADRS improvement is defined as the time, in days, from initiation of study treatment to the first observed $\geq 50\%$ decrease from Baseline in MADRS total score. Any patient who does not experience a $\geq 50\%$ decrease from Baseline in MADRS total score during the study will have their time to $\geq 50\%$ MADRS improvement censored at the time of his or her last non-missing MADRS assessment.

Time to $\geq 30\%$ MADRS Improvement (Days)

Time to $\geq 30\%$ MADRS improvement is defined as the time, in days, from initiation of study treatment to the first observed $\geq 30\%$ decrease from Baseline in MADRS total score. Any patient who does not experience a $\geq 30\%$ decrease from Baseline in MADRS total score during the study will have their time to $\geq 30\%$ MADRS improvement censored at the time of his or her last non-missing MADRS assessment.

Early Response

Early response is defined as experiencing a $\geq 50\%$ decrease from Baseline in MADRS total score along with a CGI-I score ≤ 2 at any post-Baseline visit.

Additionally, the same analysis will be repeated using $\geq 30\%$ decrease from Baseline in MADRS total score along with a CGI-I score ≤ 2 at any post-Baseline visit.

Sustained Response

Sustained response is defined as experiencing a $\geq 50\%$ decrease from Baseline in MADRS total score along with a CGI-I score ≤ 2 at Week 2 or Week 4 that continues to Week 6.

Additionally, the same analysis will be repeated using $\geq 30\%$ decrease from Baseline in MADRS total score along with a CGI-I score ≤ 2 at Week 2 or Week 4 that continues to Week 6.

Remission in MADRS (sustained or occasional)

Remission in MADRS is defined as a MADRS total score < 12.

MADRS Core Mood Items

MADRS core mood items are defined as a combination of the first two items on the MADRS questionnaire, Apparent Sadness and Reported Sadness.

Adverse Event

An adverse event is any untoward medical occurrence in a clinical study patient administered a medicinal (investigational or non-investigational) product. An adverse event does not necessarily have a causal relationship with the treatment. An adverse event can therefore be any unfavorable and unintended sign (including an abnormal finding), symptom, or disease temporally associated with the use of a medicinal (investigational or non-investigational) product, whether or not related to that medicinal (investigational or non-investigational) product.

This includes any occurrence that is new in onset or aggravated in severity or frequency from the Baseline condition, or abnormal results of diagnostic procedures, including laboratory test abnormalities.

All adverse events will be recorded on the Adverse Event CRF.

Treatment-emergent Adverse Event

Any recorded Adverse Event that occurs on or after the initiation of study treatment is considered treatment-emergent (TE). Additionally, it is assumed that an Adverse Event which was reported to have started on Day 1 without an associated onset time may have occurred after the initiation study treatment. Hence, Adverse Events occurring on Day 1 without an onset time are assumed to be TE.

Concomitant Medications

Concomitant medications are those medications taken on or after the initiation of study treatment. This definition includes medications started prior to the initiation of study treatment, but continuing concomitantly with study treatment.

Prior Medications

Prior medications are those medications taken and completed prior to the initiation of study treatment.

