A total of 44 patients (53.7%) experienced TEAEs, with the highest percentage in the paroxetine 20 mg group (65.0%, 13 patients) and the lowest in the placebo group (45.0%, 9 patients). All TEAEs were mild or moderate in intensity, with the exception of 2 severe events of nausea (MIN-117 2.5 mg: 1; paroxetine 20 mg: 1). The events of nausea were considered possibly/probably related (MIN-117 2.5 mg) and definitively related (paroxetine 20 mg) to study medication. 40.2% of patients experienced TEAEs that were considered to be related to the double-blind study medication by the investigator. For 6 patients (7.3%), TEAEs were deemed to be definitively related. Overall, 2 patients were withdrawn from the study due to adverse events occurrence (both of whom were randomized to the paroxetine 20 mg group): one female patient with severe nausea (non-serious, definitively related to the study medication) and one female patient with moderate transaminases increased (considered as an adverse event as it occurred before the start of the study medication) and moderate blood alkaline phosphatase increased (TEAE). Both events were considered unrelated to study medication.

The highest frequencies of TEAEs were reported in the system organ classes Nervous system disorders (19.5% of patients), Investigations (17.1%), Gastrointestinal disorders (12.2%), and Infections and infestations (11.0%). The most commonly reported TEAE was nausea (9.8%, 8 patients). Dizziness as well as headache were reported for 7 (8.5%) patients, and upper respiratory tract infection was reported for 4 (4.9%) patients. The remainder of reported TEAEs occurred in ≤ 3 ($\leq 3.7\%$) patients.

In general, Sheehan-Suicide Tracking Scale scores were low for all treatment groups throughout the study and no consistent pattern of change was observed.

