10.8.1. Adverse Events

The original terms used in the eCRFs by investigators to identify adverse events will be coded using the Medical Dictionary for Regulatory Activities (MedDRA). All reported adverse events with onset during the 6-week double-blind period (i.e., treatment-emergent adverse events or TEAE) will be included in the analysis. For each adverse event, the percentage of patients who experienced at least one occurrence of the given event will be summarized by treatment group.

Special attention will be given to those patients who died, or who discontinued treatment due to an adverse event, or who experienced a severe or a serious adverse event (e.g., summaries, listings, and narrative preparation may be provided, as appropriate).

A TEAE that occurs > 14 days after the date of the last dose of double-blind treatment will not be summarized.

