5.4. SAFETY ANALYSES

5.4.1. Adverse Events

Adverse events will be mapped to a Medical Dictionary for Regulatory Activities (MedDRA) version 21.0 preferred term and system organ classification. If a patient experiences multiple events that map to a single preferred term, the greatest severity grade and strongest investigator assessment of relation to study medication will be assigned to the preferred term for the appropriate summaries. Should an event have a missing severity or relationship, it will be classified as having the highest severity and/or strongest relationship to study medication.

The occurrence of TE adverse events (TEAEs) will be summarized by treatment group using preferred terms, system organ classifications, and severity. Separate summaries of TE serious adverse events (SAE), TEAE related to study treatment, TEAE leading to discontinuation of study treatment, and TE fatal adverse events will be generated. All adverse events reported will be listed for individual patients showing both verbatim and preferred terms, as well as system organ class. All adverse events that occurred prior to the

initiation of study treatment will be excluded from the tables but will be included in the listings. Any TEAE occurring after the End of Study visit will not be summarized.

Missing onset dates will be imputed as previously outlined in Section 3.3.5 as required to determine TE events. Adverse events occurring on Day 1 with missing onset times will be assumed to be TE.

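### The treatment-emergent rule works on onset date and has no clause for a pre-dose adverse event that worsens on study drug, so such a worsening may be left out of every adverse event table.

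*SAP*

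**What the plan says.** **The rule.** SAP 3.3.8 reads: "Any recorded Adverse Event that occurs on or after the initiation of study treatment is considered treatment-emergent (TE". Its tie-break for the first dosing day concerns "an Adverse Event which was reported to have started on Day 1 without an associated onset time", which it treats as treatment-emergent. SAP 5.4.1 adds: "Missing onset dates will be imputed as previously outlined in Section 3.3.5 as required to determine TE events". Protocol 10.8.1 puts the rule in terms of onset outright: "All reported adverse events with onset during the 6-week double-blind period (i.e., treatment-emergent adverse events or TEAE) will be included in the analysis".

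**The exclusion.** Under SAP 5.4.1, adverse events that precede the "initiation of study treatment will be excluded from the tables but will be included in the listings".

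**The general definition.** Just above the treatment-emergent rule, SAP 3.3.8 says of adverse events: "This includes any occurrence that is new in onset or aggravated in severity or frequency from the Baseline condition". Protocol 11.1.1 has the same sentence. The SAP fixes the reference point as follows: "Baseline will be defined as the last valid evaluation done before the study drug administration on Day 1".

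**Collection.** Protocol 11.1.1 and 11.3.1 start adverse event collection at informed consent. Patients then taper off psychotropic drugs and have at least one drug-free week before randomization. Screening lasts up to 3 weeks and can be extended to 28 days.

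**The concern.** Symptoms that begin during taper or washout will be on the adverse event form before the first dose. Some may still be present on Day 1 and then become more severe, more frequent or serious on study drug. A rule that looks only at onset has no place for that change. The general definition recognises aggravation as an adverse event, but the treatment-emergent rule does not repeat it.

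The SAP does cover the parallel case for medications. In the same section, a drug started before first dose and continued afterwards counts as concomitant. Adverse events have no matching sentence.

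Safety against placebo is a secondary objective, and the adverse event tables are its main summary. Whether a serious or severe on-treatment worsening appears in them should not depend on how a site happens to fill in the form.

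**Working it through.** No formula or stated figure bears on this point. The check sets the texts side by side and follows one event through them.

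**Step 1: which date decides?** The main sentence in SAP 3.3.8 speaks of when an event occurs, which could be read in more than one way. Three other texts settle it in practice: the Day 1 tie-break turns on when the event started, SAP 5.4.1 imputes missing onset dates in order to classify events, and protocol 10.8.1 uses onset. Classification is by the onset date on the record.

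**Step 2: is there a worsening clause?** There is none in SAP 3.3.8 (treatment-emergent definition), SAP 5.4.1 or protocol 10.8.1.

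**Step 3: which tables depend on the classification?** SAP 5.4.1 limits the overall, severity, serious, related, discontinuation and fatal summaries to treatment-emergent events. The table list in SAP section 9 agrees: 14.3.1.1 to 14.3.1.5 and 14.3.2.1 all carry that label. No table covers all serious events, all deaths or all discontinuation events regardless of onset. The only adverse event display that includes pre-dose events is listing 16.2.7.

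**Step 4: how is a worsening recorded?** Protocol 11.3.1 gives the recording instructions and does not mention worsening. Protocol 11.1.3 and 11.1.4 ask for a severity assessment and an outcome for each event, without saying what to do if severity changes. Protocol 16.6 says eCRF completion guidelines will be supplied, but they are not among these documents.

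**Step 5: follow one event.** Take a mild headache that starts on Day -5 and becomes severe on Day 4.

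| How the site records it | Onset on the record | Treatment-emergent? | Where it appears |
|---|---|---|---|
| New record for the worsening | Day 4 | Yes | All relevant tables, and the listing |
| Existing record updated to severe | Day -5 | No | Listing only |

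An insomnia record that starts on Day -7 and becomes serious on Day 20 divides the same way, with the serious-event table at stake.

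**Step 6: size.** The documents give no rate of events ongoing at Day 1 and no rate of worsening, so the number of affected patients cannot be calculated.

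**The case against.** The strongest reply rests on the general definition. Aggravation from Baseline is itself an adverse event, Baseline is the last pre-dose evaluation, and the treatment-emergent rule uses the defined term. A worsening on Day 4 is then an adverse event occurring on treatment. SAP 5.4.1 can also handle two records of one preferred term in a patient, since it takes the greatest severity and strongest relationship. This stands as far as it goes: where a new record is opened, nothing is lost. But the rule acts on recorded events and their onset dates, and nothing in the documents requires the new record.

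Other displays catch part of the loss. Reasons for discontinuation are tabulated by arm whatever the onset (SAP 5.1). Laboratory, vital-sign, ECG and C-SSRS results have their own summaries (SAP 5.4.2 and 5.4.4). Protocol 10.8.1 allows summaries, listings and narratives for deaths, discontinuations, and severe or serious events. This also stands, with limits: disposition gives a reason but not the event term, severity or relatedness, and the protocol's extra displays are optional.

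A reader might infer three stronger things that the documents do not support.

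- *That a worsening washout event can never be counted, or that all pre-dose events are excluded.* The first depends on the recording convention. The second is inexact: under SAP 3.3.5 a date with unknown day in the Day 1 month is set to Day 1, and Day 1 events without a time count as treatment-emergent.
- *That the earlier phase 2a study shows the failure.* Protocol section 1.4 describes a withdrawn patient whose raised transaminases were "considered as an adverse event as it occurred before the start of the study medication". That patient was on paroxetine and also had a counted treatment-emergent event. Both events were judged unrelated, and no on-treatment worsening is reported.
- *That the drug-placebo difference is necessarily understated.* The rule is the same in every arm. The difference shrinks only if the drug aggravates pre-existing events more than placebo does, and the documents do not show that.

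**Conclusion.** The point holds as a gap in definition. Treatment emergence is decided by onset, there is no worsening clause, and every adverse event table is limited to treatment-emergent events. An event with pre-dose onset that becomes more severe or serious on study drug may therefore be missing from all of those tables and appear only in the listing.

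This rests on one condition that the documents leave open: that the site updates the existing record instead of opening a new one. Practice could also differ between sites. The size is unknown, and any effect on the comparison with placebo is conditional. The case for acting is that a single serious event missing from its table would matter, and the correction costs very little.

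**What to change.** 1. **SAP 3.3.8:** define a treatment-emergent event as one with onset on or after first dose, or one with earlier onset that increases in severity or frequency, or becomes serious, on or after first dose.
2. **SAP 5.4.1:** exclude from the tables only those pre-dose events that did not worsen in this sense.
3. **Protocol 10.8.1:** align the wording.
4. **eCRF completion guidelines:** state that a worsening after first dose is entered as a new record with its own start date and severity. The revised definition can be programmed only if that date is captured, so this instruction belongs with it.

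The cost is a few sentences and one site instruction, with no new assessments. The downside is that counts of some common terms would rise slightly in all arms.
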